7.4 Physician Live Assessment of GL Severity

Physicians will use the [CCI](#) for direct, live comparison of the severity of the subject's glabellar lines at rest and max frown at all study visits, prior to treatment, as applicable.

The [CCI](#) includes two grading systems: one for the assessments at rest, and one for the assessments at max frown. The scale represents the severity of glabellar lines from none (grade 0), mild (grade 1), moderate (grade 2) to severe (grade 3). Each grade is also depicted by an individual photograph and a descriptive text.

Effective

Effective date: 2021-06-28 08:30

Physicians will be trained on the use of the scale, and the assessment of GL severity at rest should be performed before the assessment at max frown. See [Appendix 4](#) for physician instructions and
CCI

8 SAFETY ASSESSMENTS

AEs will be recorded in the eCRF for inclusion in the clinical database.

In addition, physicians will report all AEs non-serious, serious, and/or unexpected ADRs, and SS events to **CC1** in accordance with regulatory reporting requirements and timelines. The data will be included in the global drug safety database.

8.1 Definitions

8.1.1 Adverse Event (AE)

Any untoward medical occurrence in a patient or clinical investigation subject administered a pharmaceutical product and which does not necessarily have a causal relationship with this treatment.

An AE can therefore be any unfavorable and unintended sign (including an abnormal laboratory finding), symptom, or disease temporally associated with the use of a medicinal product, whether or not related to the medicinal product.

Thus, any new sign, symptom or disease, or any clinically significant worsening of an existing sign, symptom or disease (including new episodes of a chronic disease) compared to the condition at the first visit, should be considered as an AE.

8.1.2 Adverse Drug Reaction (ADR)

For marketed medicinal products, an ADR is a response to a drug which is noxious and unintended and which occurs at doses normally used in man for prophylaxis, diagnosis, or therapy of diseases or for modifications of physiological function.

8.1.3 Unexpected Adverse Drug Reaction (UADR)

An unexpected ADR is defined as an adverse reaction, the nature or severity of which is not consistent with the applicable study product information (e.g., medicinal package insert/summary of product characteristics for an approved study product).

8.1.4 Serious Adverse Event (SAE)

A SAE is any untoward medical occurrence that at any dose:

- Results in death,
- Is life-threatening,
- Requires inpatient hospitalization or prolongation of existing hospitalization,
- Results in persistent or significant disability/incapacity, or

- Is a congenital anomaly/birth defect.

Important medical events that may not result in death, be life-threatening, or require hospitalization may be considered a SAE when, based upon appropriate medical judgment, they may jeopardize the safety of the subject, and may require medical or surgical intervention to prevent one of the outcomes listed in this definition. Examples of such events are intensive treatment in an emergency room or at home for allergic bronchospasm, blood dyscrasia, or convulsions that do not result in hospitalization.

Note: The term “life-threatening” refers to an event in which the subject was at risk of death at the time of the event; it does not refer to an event which hypothetically might have caused death if it were more severe.

In-patient hospitalization is considered to have occurred if the subject had to stay for a night at the hospital. The criterion for prolongation of hospitalization is also defined as an extra night at the hospital. Hospitalization solely for the purpose of a diagnostic test, even if related to an AE, elective hospitalization for an intervention which was already planned before subject enrolment in the clinical study, admission to a day care facility, social admission (e.g., if the subject has no place to sleep), or an administrative admission (e.g., for an annual physical examination) may not itself constitute sufficient grounds to be considered as SAE.

8.1.5 Special Situation (SS) Events

A Special Situation (SS) event is an incidence of overdose, off-label use, medication error, occupational exposure, abuse, misuse or lack of therapeutic efficacy while using the medicinal product, or any instance of drug exposure during pregnancy or breast-feeding. A SS should be reported even if it is not associated with an adverse event.

8.2 Severity

Severity is a clinical determination of the intensity of an AE and not the severity of a disease.

The physician is to classify the intensity of AEs using the following definitions as a guideline. For this classification, the physician will take into account the possible range of the intensity of the event and report the grade of intensity which is the most appropriate according to his/her medical judgment.

Mild	Awareness of signs or symptom, but easily tolerated.
Moderate	Discomfort, enough to cause interference with usual activity.
Severe	Incapacitating with inability to work or perform usual activity.

8.3 Relationship to the Product and/or Procedure

The physician is to determine whether there is a reasonable causal relationship between the occurrence of the reaction and exposure to the product and/or the injection procedure.

Medical judgment should be used to determine the relationship, considering all relevant factors including the pattern of reaction, temporal relationships, relevant medical history, and confounding factors such as co-medication or concurrent diseases.

The expression “reasonable causal relationship” is meant to convey in general that there are facts or arguments to suggest a causal relationship (ICH E2A, Section IIIA 1).

The relationship assessment for a reaction is to be completed using the following definitions as a guidelines.

Reasonable Possibility:

According to the reporting physician, there is a reasonable possibility (i.e., suggestive evidence or arguments) that there is a causal relationship irrespective of the dose administered between:

- The product and the reaction.
- The injection procedure (injection related trauma, etc.) and the reaction.

A two-point scale (Yes or No response) shall be used for the causality assessment.

- “Do you consider that there is a reasonable possibility that the reaction may have been caused by the product?”, and
- “Do you consider that there is a reasonable possibility that the reaction may have been caused by the injection procedure?”

If either of these questions is answered Yes, the reaction is considered related, and should be reported according to the procedures outlined in Section 8.4.

No Reasonable Possibility:

No suggestive evidence or arguments can be identified regarding a causal relationship between the product or the procedure and the reaction.

8.4 Reporting Procedures

AE data will be recorded in the eCRF for inclusion in the clinical database and will be reported to CCI [REDACTED].

In addition, any ADR/UADR/SAE/SS and pregnancy must be reported immediately (within 24 hours of the physician's knowledge of the event) to the following:

CCI [REDACTED]

See [Investigator and Administrative Structure](#) for additional contact information.

In order to facilitate this reporting, the physicians will be provided with Adverse Event and Special Situation Reporting Form. If the immediate report is submitted by telephone, this must be followed by detailed written reports using the Adverse Event and Special Situation Reporting Form.

 GALDERMA		
---	--	--

8.4.1 Minimum Reporting Criteria

The following information is the minimum that must be provided to the pharmacovigilance contact within 24 hours of being aware of such adverse reactions:

- Subject identifier
- Product
- AE term and description
- Physician name and contact details

Any additional information included in the Adverse Event and Special Situation Reporting Form must be provided as soon as it is available.

The physician should report a diagnosis or a syndrome rather than individual signs or symptoms. The physician should also try to separate a primary AE considered as the foremost untoward medical occurrence from secondary AE which occurred as complications.

8.5 Pregnancy

Pregnancy itself is not regarded as an adverse reaction unless there is a suspicion that the product has interfered with a contraceptive method. If pregnancy occurs while using the product, the outcome of the pregnancy will then need to be collected. This applies to whether or not the pregnancy is considered to be related to interference of the product with a contraceptive method.

Any pregnancy complication or elective termination of a pregnancy for medical reasons will be reported as an AE or SAE.

Abnormal pregnancy outcomes (e.g. spontaneous abortion, foetal death, stillbirth, congenital anomalies, ectopic pregnancy) are considered SAEs and will be reported as such.

Information regarding pregnancies must be manually collected on the Drug Exposure for Pregnancy Form, item 1 to 19.

Outcome information should also be collected on the Drug Exposure for Pregnancy Form, item 20 to 29. Drug Exposure for Pregnancy Form must be reported to CCI immediately (within 24 hours of the physician's knowledge of the event).

The physician must instruct all female subjects to inform them immediately should they become pregnant while using the product. The physician should counsel the subject, discussing the risks of continuing with the pregnancy and the possible effects on the fetus.

8.6 Appropriateness of Measurements

The satisfaction questionnaires are tools that have been developed in order for the Sponsor to better understand the subject and physician needs and expectations with respect to *Dysport* treatment and the treatment regimen.

Effective

Effective date: 2021-06-28 08:30

The other efficacy measurements used in this study are considered standard measurements, and are generally recognized as reliable, accurate, and relevant. **CCI**

[REDACTED]

9 CLINICAL STUDY VISITS DESCRIPTIONS AND PROCEDURES

9.1 Description of Clinical Study Visits

Please refer to the schedule of assessment table ([Table 2](#)).

The decision to administer *Dysport* must be made by the treating physician before including the subject in the study and has to be clearly separated and independent of the decision to include the subject in the study.

The treatment regimen will be performed according to the approved leaflet in China and the physician's real clinical practice.

9.1.1 Screening (≤ 30 days of Baseline/Injection 1)

NOTE: Screening and Baseline/Visit 1 (i.e., Injection 1) may be performed on the same day. If performed as separate visits, informed consent, demographic data, and medical history should be complete at Screening, and all other remaining visit procedures and confirmation of subject medical history should be performed at Baseline/Visit 1 (i.e., Injection 1).

1. Review and explain the nature of the study to the subject.
2. Obtain the signed and dated ICF prior to performing any study-related evaluations and/or procedures. Provide a fully completed dated and signed copy to the subject.
3. Collect information regarding demographics, relevant medical history, previous therapies and procedures, and concomitant medications and procedures in accordance with the physician's real clinical practice.

9.1.2 Injection Visits / Visits 1, 3 and 5 (3-6 months apart)

1. If Screening is performed as a separate visit, confirm subject medical history.
2. Subject to complete self-assessment of glabellar line severity at max frown using the 4-point Categorical Scale. See Section [7.3](#) and [Appendix 3](#).
3. Subject to complete the Subject Satisfaction Questionnaire. See [Appendix 1](#).
4. Physician to complete assessment of the subject's glabellar line severity at rest and max frown using [CCI](#) [REDACTED]
5. Physician to complete the [CCI](#) [REDACTED]. See [Appendix 2](#).
6. Physician or designee to prepare *Dysport* treatment for the subject. See Section [6.1.5](#).
7. Prior to injection, clean the subject's treatment area with a suitable antiseptic solution. See Section [6.1.5](#).
8. The physician will administer *Dysport* treatment. See Section [6.1.5](#).

9. The physician will document injection practice details including muscle(s) injected, total dose and volume, dose and volume per injection point, and number of injection points.
10. Physician or designee will ask the subject about reactions, and document in accordance with the physician's real clinical practice.
11. Schedule the subject's follow up visit three weeks (± 7 days) from the date of injection.

9.1.3 Follow up Visits / Visits 2, 4, and 6 (three weeks (± 7 days) from last injection visit)

1. Subject to complete self-assessment of glabellar line severity at max frown using the Static 4-point Categorical Scale. See [7.3](#) and [Appendix 3](#).
2. Subject to complete the Subject Satisfaction Questionnaire. See [Appendix 1](#).
3. Physician to complete assessment of the subject's glabellar line severity at rest and max frown
CCI [REDACTED]
4. Physician to complete the Physician Satisfaction Questionnaire. See [Appendix 2](#).
5. Physician or designee will ask the subject about reactions, and document in accordance with the physician's real clinical practice.
6. Schedule the subject's next visit three to six months from the date of the injection visit.

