7.5. Safety Analysis

AEs will be coded by MedDRA version 25.1. SOC and PT will be presented in summary tables of AE. All summary table will be based on Treatment Emergent AE (TEAE).

TEAE defines as all AEs that occur after the first treatment.

Overall TEAEs, UAEs, SAEs, SS Events, AEs leading to discontinuation from study, AEs leading to death and whether these AEs are possibly caused by the product and/or injection procedure, will be summarized by number of events, number of subjects, percentage and 95% CI.

The number of events, number of subjects and percentage with AEs and product and/or injection procedure related AEs will be summarized for each category by SOC, PT and severity. If multiple

AEs in the same SOC (PT) have occurred in the same subject when summarizing the number of subjects, the subject will be counted only once for this SOC (PT). When summarizing the number of subjects by severity, if multiple AEs in the same SOC (PT) have occurred in the same subject, the event with the highest severity of this SOC (PT) will be used for analysis. When summarizing the number of events, all the AEs will be accounted.

Detailed information of AEs, UAEs, SAEs, SS Events, AEs possibly caused by the product and/or injection procedure, AEs leading to discontinuation, and AEs leading to death will be listed by subject.

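### Visit steps prompt for 'reactions' while the safety analysis counts all adverse events, so events not linked to treatment could be under-recorded

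*Protocol*

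**What the plan says.** **Visit steps.** At Visits 1, 3 and 5 (Protocol 9.1.2), step 8 reads "The physician will administer *Dysport* treatment". Step 10 reads "Physician or designee will ask the subject about reactions", continuing "and document in accordance with the physician's real clinical practice". The same instruction is step 5 for Visits 2, 4 and 6 (9.1.3) and step 5 for Visit 7 (9.1.4). The self-assessment, questionnaire and injection steps refer the reader to a section or appendix. The reactions step refers to nothing.

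**Definition and recording.** Protocol 8.1.1 defines an AE as an untoward occurrence "which does not necessarily have a causal relationship with this treatment", and SAP 4.2.1 repeats this. Protocol 8 states that "AEs will be recorded in the eCRF for inclusion in the clinical database". Section 8.4 repeats the eCRF rule, and 12.6.2 asks for thorough documentation of all AEs. Table 2 (SAP 3.3) marks a Safety Review at all seven visits. Its prior-to-injection footnote is attached to the severity and satisfaction rows but not to the Safety Review.

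**Analysis.** SAP 7.5 bases its summary tables on treatment-emergent AEs (TEAEs), meaning all AEs after the first treatment. It reports events, subjects, percentages and 95% confidence intervals for the overall categories. SAP 7.7 drops the adverse drug reaction category and widens unexpected reactions to unexpected events.

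**The concern.** The safety outcome includes events unrelated to treatment, but the only described prompt uses a word that a subject or physician may take to mean effects of the injection. A subject asked about reactions could leave out an illness that they do not connect with the product. These unrelated events are what separate an AE count from a drug-reaction count, and they fill the category of no reasonable causal possibility in Protocol 8.3. If they go unmentioned, the incidences in SAP 7.5 could be too low and the related share too high. Because documentation follows each physician's own practice, completeness could also differ among the 10 centres. The visible SAP text plans no AE table by centre that would show this.

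A second, smaller issue is order. At Visits 3 and 5 no step before the injection asks about events since the previous visit. One later prompt therefore has to cover both that interval and the minutes after the new injection.

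**Working it through.** Neither document states an expected AE rate or a capture rate, and the sample size of about 250 is declared not to be calculated. There is no planned figure to reproduce. The check is a comparison of text and two short calculations.

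**1. Which text governs what**

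| Place | Governs | Scope |
|---|---|---|
| Protocol 9.1.2 step 10, 9.1.3 step 5, 9.1.4 step 5 | What the subject is asked | Reactions, written up by local practice |
| Protocol Table 2, SAP 3.3 | That a Safety Review takes place at Visits 1 to 7 | Content not defined in the visible text |
| Protocol 8 and 8.4 | Recording and reporting | All AEs |
| Protocol 12.6.1 and 12.6.2 | Source and eCRF documentation | All data, all AEs |
| Protocol 8.1.1, SAP 4.2.1 | Definition | Any cause |
| SAP 7.5 | Tables | All AEs after first treatment |

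Only the first row says what is asked. The recording duties apply once the site knows of an event; they do not bring an unmentioned event to light.

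**2. What 'reaction' means in the Protocol**

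- Causal use: in 8.1.2 "an ADR is a response to a drug which is noxious and unintended". In 8.5, a pregnancy counts as an adverse reaction only if interference by the product with contraception is suspected.
- Neutral use: 8.3 applies the word to events whose causality is still to be judged, including those then judged to have no reasonable link.

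The word has no fixed meaning, so a site can read the visit step either way.

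**3. Interval covered by the prompt at Visits 3 and 5**

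Inputs from Table 2: follow-up at 3 weeks ± 7 days (2 to 4 weeks) after an injection; next injection at 3 to 6 months, with 1 month = 4 weeks (12 to 24 weeks).

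- Shortest gap since the previous scheduled visit: 12 − 4 = 8 weeks.
- Longest gap: 24 − 2 = 22 weeks.

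Visits 2 and 4 carry the same prompt, so the first 2 to 4 weeks after each injection have already been asked about.

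**4. Illustration of size (assumed inputs)**

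Assume 250 subjects in the Safety Set, a true share *p* with at least one TEAE, and a fraction *c* of those subjects with one recorded. Recorded subjects *x* = 250 × *p* × *c*, rounded to a whole number (halves to even). The intervals are exact (Clopper-Pearson) 95% intervals; SAP 7.5 names no method for AEs, so this too is an assumption.

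| True *p* | *c* | *x* | Recorded % (95% CI) | Covers *p*? |
|---|---|---|---|---|
| 10% | 0.9 | 22 | 8.8 (5.6–13.0) | yes |
| 10% | 0.8 | 20 | 8.0 (5.0–12.1) | yes |
| 10% | 0.7 | 18 | 7.2 (4.3–11.1) | yes |
| 20% | 0.9 | 45 | 18.0 (13.4–23.3) | yes |
| 20% | 0.8 | 40 | 16.0 (11.7–21.1) | yes |
| 20% | 0.7 | 35 | 14.0 (9.9–18.9) | no |
| 40% | 0.9 | 90 | 36.0 (30.0–42.3) | yes |
| 40% | 0.8 | 80 | 32.0 (26.3–38.2) | no |
| 40% | 0.7 | 70 | 28.0 (22.5–34.0) | no |

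At 90% capture the loss stays within sampling error in all three rows. At 70% the interval excludes the true value when that value is 20% or 40%, but not when it is 10%.

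**The case against.** The strongest reply is that the visit step is not the whole safety plan. Section 9.1 opens by referring sites to Table 2, which has a Safety Review at every visit. Section 8 sets out definitions, causality assessment and reporting, and 12.6 requires data in source documents and the eCRF. The step names a topic and gives no script. The eCRF and the Data Management Plan, which are not in the documents, may prompt for AEs directly. Serious AEs are defined without regard to cause and must be reported within 24 hours of the physician's knowledge. The study is descriptive, and its visible primary and secondary endpoints concern satisfaction.

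Much of this stands, and it rules out four stronger readings that a reader might infer:

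- *That the Protocol collects only drug reactions.* It does not: Sections 8, 8.4 and 12.6.2 require all AEs to be recorded, and 8.3 uses 'reaction' for events not judged related.
- *That AE incidences will be biased low.* The documents give no capture rate; they support a risk, not a prediction.
- *That the whole 12 to 24 weeks since the last injection go unasked until after re-injection.* Visits 2 and 4 ask at 2 to 4 weeks, which leaves 8 to 22 weeks.
- *That the order of steps lowers AE totals.* The prompt is still given at the same visit, TEAEs are counted from the first treatment, and the visible SAP text has no AE table by injection cycle. The text also does not bar asking earlier, and at Visit 1 a prompt after the injection is natural.

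The reply does not fill the gap in elicitation. Table 2 names a Safety Review without describing it, and the other sections govern recording. The only operational instruction in the visible text uses the narrower and inconsistent word.

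**Conclusion.** The point holds as a risk. The visit steps are worded more narrowly than the AE definition and the SAP tables, and no other visible text says how AEs are elicited. AEs that subjects do not link to treatment could be under-recorded, with completeness varying by centre. Serious AEs are less exposed because of the separate 24-hour duty, although that duty also depends on the physician learning of the event.

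The size cannot be derived from the documents. With 250 subjects and the assumed rates above, the effect runs from negligible to large enough for the confidence interval to exclude the true incidence. The order at Visits 3 and 5 is a lesser matter of onset date and attribution to the right injection. The satisfaction endpoints are not affected. The change is worth making because it is cheap and bears on every AE table. The conclusion assumes that the eCRF and site training do not already supply an open AE prompt; if they do, only the Protocol wording needs aligning.

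**What to change.** Reconcile Protocol 9.1.2 step 10, 9.1.3 step 5 and 9.1.4 step 5 with Section 8 and SAP 7.5:

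- Use one open, non-leading question at every visit on any new or worsened health problem since the last visit.
- Have every answer that meets the AE definition entered in the eCRF regardless of causality, and cite Section 8.4 in the step.
- At Visits 3 and 5, ask the question before the injection and record post-injection events separately. This changes data collection only, not treatment.
- Define Safety Review in Table 2 by reference to this step.

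If visits are already complete, describe in the clinical study report how AEs were elicited, including any eCRF prompt, and state possible under-recording of unrelated events as a limitation of the SAP 7.5 tables.

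The cost is minor rewording, brief site training and a few more AE records. The sample size does not change.
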